7.2.3 Additional contact

In addition to the contact with study team members during the scheduled intervention and follow-up assessment sessions, participants will be contacted approximately every 2-4 weeks (and additionally as needed for engagement purposes) to “check in”, to inquire about how the study is going for them and if they have any questions, and answer questions they may have. Participants who had undergone the videorecorded activity and are interested in receiving this material will be mailed a DVD with his/her own video recordings after their study completion.

8 Study Analysis

8.1 Sample Size Determination

We conservatively estimate the need to screen approximately 4,000 individuals to enroll up to 800 participants. In our pilot RCT of MM for opioid-treated CLBP, 304 potential participants were identified through the EHR data and clinician and self-referrals; 87 were screened, 48 were eligible and 35 were enrolled.¹⁷ During the 26-week pilot study, no participant withdrew, and two (5.7%) missed the final assessment. In the PI’s other trial of MM, 92% of 123 alcohol dependent adults completed a 1-year follow-up.⁴⁷ Our other studies have also had excellent recruitment and retention. Two RCTs of MM led by [name] had an overall 95% (540/567) retention rate over a 9 month follow-up. For these studies, 2,080 adults were screened, 183 were found eligible but declined and 567 (27.3%) were enrolled.^{46,48}

Using estimates from systematic reviews and meta-analyses, comparing MM and CBT to a wait-list controls,^{10,18-20,35} and from two previous trials of MM in opioid-treated chronic pain,^{15,17} as outlined in the Background, we assume an effect size $d=0.25$ of MM vs CBT for pain severity and function, and a dropout rate of not more than 20%. We adjust for multiplicity of the co-primary outcomes by using a significance level of 0.025 for each Aim 1 outcome, for an overall significance level of at most 0.05. With 383 participants randomized to each of the treatment arms (766 total), a two-sample test with a significance level 0.025 and at most a 20% dropout rate is powered to detect an effect size of 0.25 of MM versus CBT for primary outcomes with power of 0.80.

To assess power to detect treatment differences between the proposed subgroups, we used the sample size of N=383 per group and a significance level $\alpha=0.05$ (i.e., not adjusting for multiplicity). Based on the existing literature and prior studies by Co-Investigators, we anticipate that approximately 35% of the study participants will show an elevated level of negative affect and approximately 45% of the sample will have an elevated level of opioid-related aberrant drug use

behaviors. For the power to assess Aim 3, we wish to be able to detect a difference of 0.5 (moderate effect size) between the subgroups, assuming no effect for the subgroup with less pathology (lower HADS [score ≤ 11]^{42,67} or COMM [score < 9]⁶⁸ scores) and an effect size of 0.5 for the intervention effects in the subgroup with elevated negative affect and/or opioid misuse scores. The proposed subgroup analyses are based on the assumptions for the prevalence of elevated scores of negative affect (score > 11 on the HADS) and opioid misuse behaviors (score ≥ 9 on the COMM) that indicate a person's increased risk for anxiety, depression or opioid use disorders.^{42,43,68} We chose the effect size of 0.5 for the proposed subgroup analyses per existing recommendations; this doubles the proposed main effect size of the study, assumed to be 0.25, for the subgroup hypothesized to benefit most from the intervention.⁶⁹ Based on the statistical simulations of size 10,000 (so that the margin of error is approximately 0.01) we conducted, we will have at least 80% power (84% for negative affect subgroup and 86% opioid misuse subgroup) to detect a significant (subgroup \times treatment) interaction effect for each of these two main subgroups.

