| Main Inclusion Criteria | Moderate to severe chronic low back pain treated with \geq 15 mg/day of morphine-equivalent opioid dose for \geq 3 months; age 21+ |
| Main Exclusion Criteria | Prior formal MM or CBT training; inability to safely or reliably participate; current pregnancy; pre-existing borderline personality, delusional or bipolar (manic) disorders ("active" in the prior 12 months). Competent adults, meeting eligibility criteria, will be able to participate regardless of gender, race, ethnicity, religion or socioeconomic status. Prisoners, pregnant women and mentally impaired persons will not be included. Children, per eligibility criteria, are not eligible. |
| Study Interventions | Two behavioral therapies: Mindfulness Meditation and Cognitive Behavioral Therapy, delivered in addition to "usual care" |
| Intervention Duration | Both MM and CBT interventions will consist of 8 weekly two-hour therapist-led group-therapy sessions (total 16 hours); in addition, participants will be asked to engage in home practice of either MM or CBT techniques for at least 30 minutes/day, 6 days/week during the 12-month study. |
| Statistical Methodology | Primary outcome analysis: Intention-to-treat analysis in the framework of linear mixed effects to examine the comparative effectiveness of treatment on the change in pain severity, function (Aim 1) and quality of life scores and opioid dose (Aim 2) over 12-months between the two groups. Qualitative analysis for qualitative data. |

Schematic of Study Design

Contents

| | |
|---|----|
| Study Summary | 10 |
| Schematic of Study Design | 11 |
| 1 Key Roles | 15 |
| 2 Background and Introduction | 18 |
| 2.1 Background and Rationale | 18 |
| 2.2 Hypotheses | 18 |
| 2.3 Study Interventions | 19 |
| 2.4 Summary of Relevant Clinical Data | 19 |
| 2.5 Potential Risks and Benefits to Participants | 21 |
| 2.5.1 Known Potential Risks | 21 |
| 2.5.2 Protection Against Risks | 21 |
| 2.5.3 Potential Benefits to Participants | 18 |
| 3 Study Objectives and Purpose | 23 |
| 4 Study Design and Endpoints | 23 |
| 4.1 General Design | 23 |
| 4.1.1 Primary Study Endpoints | 24 |
| 4.1.2 Secondary Study Endpoints | 24 |
| 5 Study Participants – Enrollment and Withdrawal | 24 |
| 5.1 Participant Population | 25 |
| 5.2 Inclusion Criteria | 25 |
| 5.3 Exclusion Criteria | 25 |
| 5.4 Participant Screening for Recruitment | 26 |
| 5.4.1 Participant Identification | 26 |
| 5.4.2 Recruitment and Retention Strategies | 26 |

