
5.4.2 Recruitment and Retention Strategies

Our patient, family and community advisors, including the CARDS group; staff from the Wisconsin Network for Research Support; and Investigators with expertise in engaging patients have advised on the recruitment strategies and materials.

Potential participants identified via health record-based data search or by their clinicians will be mailed letters with an opt-out/response card (see section 5.4.1. for details). Those who do not return these cards within the pre-specified time period will be contacted by the study coordinator by phone. Potential participants will also be able to call the research coordinator directly using the contact information found in the study brochure, website or other advertising.

During the initial screening conversation by phone or in person, study coordinators will read an informational statement about the study and about the risks and rights as a participant, in particular the right to cease participation at any time without any repercussion or loss of benefits. The coordinator will also ask if the potential participant has any questions about the study and will answer questions they may have before seeking a verbal consent to proceed with eligibility screening. Those ineligible or uninterested will be offered information about MM and CBT therapy options. Interested eligible persons will be invited to a virtual or in-person meeting with the study coordinator to go over the details of study participation, review an informed consent and authorization for the use of health information form (one combined form) and provide oral (or written, for in-person meetings) consent. The participant will receive a copy of the consent form for their records. When a participant provides written consent, a copy will also be kept as part of the study records; for oral consent, the provision of consent will be indicated in the study records. All participants will be informed that their participation is voluntary, of their right to withdraw at any time for any reason, and will be encouraged to ask questions at any time.

We conservatively estimate the need to screen 4,000 individuals to enroll up to 800 participants within the first 4 years of the study, with the assumption that the attrition rate will not exceed 20%. These assumptions and estimates were based on previous research conducted by the PI and Co-Is, and the results of sample size calculation (see Appendix).

Retention

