Both MM and CBT interventions have been patterned after existing programs^{21,22,24,64,65} and adapted to meet the needs of patients with opioid-treated CLBP, with input from content experts and patient advisors who were participants in the PI's pilot RCT.³⁶ These interventions will be matched in terms of duration, setting and contact time to limit *intervention bias*. Each intervention will follow a written manual and be delivered by a trained therapist with at least one other research staff member or clinician present or easily accessible by phone over 8 weeks (weekly two-hour group sessions). In-person delivery will take place in a clinical, research- or community-based facility. When remote participation in the study activities (e.g., intervention sessions, assessment visits) is needed, the telehealth delivery will take place via an approved, secure, HIPAA-compliant platform (e.g., WebEx, HIPAA-compliant Zoom, etc.) or by phone. In addition, participants will be asked to practice MM or CBT strategies at home for at least 30 minutes/day, 6 days/week during the 12-month study and log their practice minutes. The session format will be comparable between the interventions. Each session will start with the review of home practice, experiences, concerns and questions, followed by a MM or CBT exercise, then introduction to the session-specific core concepts and 2-3 MM or CBT exercises (concept application), each followed by discussion of participant experiences and MM skills for coping with challenges related to opioid-treated CLBP. This interactive format will enable monitoring and enhancement of participant treatment receipt and enactment, essential elements of *treatment fidelity*. Each session will end with a review of the home practice for the following week. These methods and targets are feasible.^{16,17,47,66} The outline of the MM and CBT interventions is attached in Appendix.

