During the virtual meeting at baseline, eligibility will be confirmed. Eligible, interested individuals will complete the verbal informed consent procedures and be assigned a study ID number (approximately 20 minutes to complete, on average). Then they will complete verbally or electronically the baseline questionnaires (approximately 55 minutes to complete, on average), followed by a brief videorecorded activity (approximately 9 minutes to complete), which will only involve a brief interview about the impact of back pain and opioid therapy, and expectations/impact of the study. Then participants will be randomized (1:1 block scheme prepared by the study statistician) to the MM or CBT groups, and receive information about details and scheduling of their respective interventions. All baseline questionnaires will be completed verbally, electronically, or on paper if the participant requests it.

Intervention Sessions

Participants in each intervention group will be asked to attend eight weekly 2-hour sessions of their respective intervention, practice the intervention-taught techniques at home (at least 30 minutes/day; 6 days/week during the 12-month study), and log/report their home practice. The standardized form for collecting the home practice data is attached in Appendix. Intervention sessions will be audio-recorded and monitored/audited for fidelity. In each course's final session, participants will fill out a survey (see Appendix) reflecting on their intervention- and study-related experiences. The content for both the in-person and virtual versions of the interventions is the same. They are both delivered in group format, both include a break halfway through, and both encourage active participant engagement and discussion.

In-person sessions

In-person intervention sessions will occur in a group format in a clinical, research, or community-based location. Participants will receive hard copies of the intervention materials in the first class they attend. Home practice and intervention session specific materials will be collected during the in person sessions when possible.

Virtual sessions

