8.2 Statistical Methods

There are no planned interim analyses for this minimum-risk study. Primary, secondary, and exploratory analyses will be tested in the framework of linear mixed effects to examine the comparative effectiveness of treatment on the change in pain severity, function (Aim 1) and QoL scores and opioid dose (Aim 2) over 12-months between the two groups. Tests will be performed at a two-tailed significance level of 0.025 for each co-primary outcome (Aim 1) and a 0.05 significance level for the secondary outcomes (Aim 2). Contrasts will be used to test for an overall treatment effect at 6 and 12 months. Detailed Statistical Analysis Plan is located in Appendix.

If and only if, the planned superiority analysis does not find statistically significant differences between the two groups, we will employ a formal non-inferiority analysis as a pre-specified secondary analysis. This analysis would employ mixed effects models to determine 95% confidence intervals for the difference between the mean scores of the primary outcomes of pain (BPI) and function (ODI) between the two groups, with the purpose of assessing whether MBT is non-inferior to CBT for treatment of people with opioid-treated chronic low back pain, using acceptable difference delta values of 0.8 for the BPI pain scale and 8.0 for the ODI function scale.

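### The power of 0.80 in Section 8.1 assumes independent participants although both arms are treated in therapist-led groups; no group size, ICC or therapy-group term is stated

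*Combined protocol and SAP*

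**What the plan says.** Section 8.1 (Sample Size Determination) takes d = 0.25 for both co-primary outcomes, a significance level of 0.025 for each, and a dropout ceiling of 20%. It concludes that with 383 randomised per arm (766 in total) "a two-sample test with a significance level 0.025 and at most a 20% dropout rate is powered to detect an effect size of 0.25" with power 0.80. It mentions no group size, number of groups, ICC or design effect.

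Delivery is by group in both arms. The Study Summary (Intervention Duration) specifies "8 weekly two-hour therapist-led group-therapy sessions (total 16 hours". Section 6 says of the sessions: "This interactive format will enable monitoring and enhancement of participant treatment receipt and enactment". Section 7 (Intervention Sessions) says that the in-person and virtual formats "both encourage active participant engagement and discussion". Randomisation is of individuals, 1:1, stratified by site (Section 6.2).

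Section 8.2 (Statistical Methods) says the analyses will be "tested in the framework of linear mixed effects to examine the comparative effectiveness of treatment on the change in pain severity" and the other outcomes. It names no random effect of any kind and adds: "Detailed Statistical Analysis Plan is located in Appendix". Section 5.4.2 likewise refers to an appendix for the sample-size calculation. Neither appendix is in the text available for this review.

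**The concern.** Participants are randomised one by one but then spend 16 hours with the same therapist and the same fellow participants. Therapist skill, group climate and shared discussion can make outcomes within a group more alike than outcomes across groups. Since both arms are grouped, any such correlation inflates the variance of the treatment difference from both sides.

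Two separate things are at stake.

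- **Power.** A figure computed under independence overstates the power the design delivers, whatever model is fitted later. This matters when a non-significant superiority result is read, and under Section 8.2 that result triggers the non-inferiority analysis.
- **Error rate and interval width.** Only if the fitted model also leaves out therapy group would the co-primary tests exceed 0.025 and the 95% intervals be too narrow.

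**Working it through.** **Inputs from the documents.** d = 0.25, 0.025 per co-primary outcome, two-sided (8.1, 8.2); 383 per arm and at most 20% dropout (8.1); enrolment of up to 800, i.e. 400 per arm (4.1); "92% of 123 alcohol dependent adults completed a 1-year follow-up" in an earlier trial (8.1); non-inferiority margins of 0.8 BPI and 8.0 ODI points (8.2); pilot baseline SDs of 1.4 and 11.4 (2.4).

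**Assumptions, not in the documents.** 8 randomised per group (range 6 to 12); ICC 0.01, 0.02, 0.05.

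**Step 1: the plan's figure.** The two-sample t-test needs 305.4 per arm for power 0.80, so 306. With 306 per arm the noncentral t gives 0.801. Dropout: 306/0.8 = 382.5, so 383. This matches exactly. The completers expected are 383 × 0.8 = 306.4, so the room left for a design effect is 306.4/305.4 = 1.003 (or 306.4/304.2 = 1.007 by the normal approximation). The figure therefore contains no allowance for clustering.

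**Step 2: adding clustering.** Design effect DE = 1 + (m − 1) × ICC, where m is the analysed group size; effective n = completers/DE. For 8 per group at 20% dropout, m = 8 × 0.8 = 6.4:

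| ICC | DE | Effective n per arm | Power |
|---|---|---|---|
| 0.01 | 1 + 5.4 × 0.01 = 1.054 | 306.4/1.054 = 290.7 | 0.778 |
| 0.02 | 1.108 | 276.5 | 0.755 |
| 0.05 | 1.270 | 241.3 | 0.690 |

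Groups of 6 (m = 4.8) give 0.785 / 0.769 / 0.722, and groups of 12 (m = 9.6) give 0.765 / 0.729 / 0.633. Using the full group size of 8 after dropout instead of 6.4 would give 0.773 / 0.744 / 0.663, so the table uses the milder convention.

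**Step 3: offsets, 8 per group.** Break-even ICC = (completers/305.4 − 1)/(m − 1), the largest ICC at which power is still 0.80.

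| Scenario | Power at ICC 0.01 / 0.02 / 0.05 | Break-even ICC |
|---|---|---|
| 383 per arm, 80% retained | 0.778 / 0.755 / 0.690 | 0.0006 |
| 383 per arm, 92% retained | 0.834 / 0.810 / 0.740 | 0.024 |
| 400 per arm, 80% retained | 0.797 / 0.775 / 0.711 | 0.009 |
| 400 per arm, 92% retained | 0.851 / 0.828 / 0.760 | 0.032 |

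Baseline adjustment, for which 8.1 takes no credit, multiplies the variance by (1 − ICC)(1 − r²) + m × ICC if the group variance is not reduced. With 383 per arm and 80% retained, an assumed baseline–outcome correlation of r = 0.3 gives 0.817 / 0.793 / 0.724, and r = 0.5 gives 0.885 / 0.861 / 0.787. This gain exists only if d = 0.25 is in raw-score SD units, not change-score SDs.

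**Step 4: only if no group term is fitted** (8 per group, 20% dropout). Type I error = 2 × (1 − Φ(2.241/√DE)) = 0.029 / 0.033 / 0.047 against 0.025. The 95% intervals are 1/√DE of the correct width, i.e. 2.6% / 5.0% / 11.3% too narrow. For non-inferiority, the half-width is 1.96 × SD × √(2/306.4). At ICC 0.05 it grows by √1.270:

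- BPI, SD 1.4: 0.222 to 0.250, a shift of 0.028 (3.5% of 0.8). SD 2 (assumed): 0.317 to 0.357, a shift of 0.040 (5.0%).
- ODI, SD 11.4: 1.81 to 2.03, a shift of 0.23 (2.9% of 8.0). SD 16 (assumed): 2.53 to 2.86, a shift of 0.32 (4.0%).

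**The case against.** The strongest counter-arguments are these.

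- **The model may already be right.** Section 8.2 is a summary and lists no random effects at all, not even one for participant, so its silence on therapy group shows little. This stands: Step 4 is conditional and no error in the analysis can be asserted. It does not touch the power figure, because a group term protects the type I error but does not restore power computed under independence.
- **20% dropout is a ceiling.** Section 8.1 also cites 95% retention (540/567) in two 9-month trials. With 8 per group and 383 per arm, 95% retention gives 0.846 / 0.822 / 0.75 and a break-even ICC of about 0.029. Nor is 0.80 a cliff: at ICC 0.01 and the full 20% dropout the loss is about two points, and any sample size rounded to its target leaves almost no headroom. All of this is fair and is why the trial may be adequately powered.
- **The 6- and 12-month contrast may add precision.** If it averages the two visits, which 8.2 does not make explicit, an assumed within-person correlation of 0.6 to 0.7 gives 0.86–0.84 / 0.84–0.82 / 0.77–0.75 at 20% dropout. Section 8.1 does not claim this gain. Taken one at a time, this and the other offsets shown leave power below 0.80 at ICC 0.05 with 8 per group, although they could be combined.
- **It is late.** The version history reaches V18 (October 2020), with enrolment planned for the first four years, so restating power changes no recruitment decision. A non-significant result is read mainly from its confidence interval. This limits the practical weight, but the interval itself depends on the model, which should be confirmed.

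**Conclusion.** The concern holds. That 8.1 contains no clustering allowance is certain, since its figure reproduces exactly under independence. The size of the consequence is uncertain, because the documents give neither group size nor ICC. With an assumed 8 per group, the stated 0.80 at the stated 20% dropout survives only an ICC below about 0.001. It survives an ICC of about 0.024 at 92% retention, and about 0.032 if 800 are also enrolled. Over groups of 6 to 12 and ICC 0.01 to 0.05, power at 20% dropout runs from 0.785 down to 0.63.

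The defect is one of disclosure: 8.1 does not let a reader judge whether the trial is adequately powered. The error-rate and interval consequences arise only if the SAP appendix also lacks a group term, and the effect on the non-inferiority conclusion would then be small, about 3–5% of the margins at ICC 0.05. This should be fixed; confidence is medium.

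**What to change.** **Section 8.1.** State the planned group size. In place of the single 0.80, give power for d = 0.25 over a plausible ICC range (for example 0.01 to 0.05), at 20% dropout and at expected retention. It would help to say whether d is in raw-score or change-score SDs and whether baseline adjustment is counted.

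**Section 8.2 and the SAP.** Specify, or confirm if the appendix already does so, a random intercept for the scheduled therapy group in both arms, with site as a fixed effect and Kenward-Roger or Satterthwaite degrees of freedom. Use the same model for the non-inferiority intervals. A therapist effect is optional, as a sensitivity analysis, if there are enough therapists to support it.

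**Cost.** SAP wording and one restated figure. Group membership comes from the scheduled course and the attendance log (Section 11.4), so no new data are needed. Coded group identifiers need not reveal which arm is MM, so the analyst blinding in Section 6.2 can be kept. The downside is slightly wider intervals and a less favourable stated power. Enrolment does not change.

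### Do the 84% and 86% power figures for Aim 3 in Section 8.1 conflict with the inputs given for them?

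*Combined protocol and SAP*

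**What the plan says.** Section 8.1 sizes the trial on Aim 1. It randomizes 383 participants to each arm (766 in total), tests each co-primary outcome at 0.025, and states that the design with "at most a 20% dropout rate is powered to detect an effect size of 0.25 of MM versus CBT" has power 0.80.

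The next paragraph turns to Aim 3. It says that "we used the sample size of N=383 per group and a significance level" of 0.05, with the remark "i.e., not adjusting for multiplicity". It expects that "approximately 35% of the study participants will show an elevated level of negative affect and approximately 45% of the sample" will have elevated opioid misuse behaviours. The target is "a difference of 0.5 (moderate effect size) between the subgroups, assuming no effect for the subgroup with less pathology", together with "an effect size of 0.5 for the intervention effects in the subgroup with elevated negative affect and/or opioid misuse scores". The value 0.5 is explained by noting that "this doubles the proposed main effect size of the study, assumed to be 0.25". The power, from 10,000 simulated trials with a margin of error of about 0.01, is given as "84% for negative affect subgroup and 86% opioid misuse subgroup". The paragraph does not mention dropout.

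**The concern.** Three features of the Aim 3 paragraph catch the eye.

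- **Sample size.** The paragraph names 383 per group as its input. With 383 analysed per arm, the power is about seven points above the reported values. That is far outside the stated simulation margin of about one point.
- **Effect sizes.** An effect of 0 in one subgroup and 0.5 in the other averages to 0.25 only if half the participants are in the elevated subgroup. The plan expects 35% and 45%, yet it mentions 0.25 as the main effect a line or two later.
- **Subgroup definition.** The wording in "an effect size of 0.5 for the intervention effects in the subgroup with elevated negative affect and/or opioid misuse scores" could be read as one combined subgroup, although the prevalences and powers are given for each moderator separately.

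If these were real errors, the power claim for Aim 3 would be unsupported, or the Aim 1 and Aim 3 assumptions would contradict each other. Either would cast doubt on the sample size.

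**Working it through.** **Inputs, all from Section 8.1 unless noted.** 383 randomized per arm; dropout at most 20%; prevalence p = 0.35 and p = 0.45; difference in treatment effect between subgroups 0.5; alpha 0.05 for Aim 3; overall effect 0.25 and alpha 0.025 for Aim 1; 1:1 allocation (Section 6.2). Two inputs are assumed because the Aim 3 paragraph does not give them: a two-sided test (Section 8.2 states two-tailed testing for the co-primary outcomes) and effects in units of a standard deviation of 1.

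**Step 1: what 383 means.** The Aim 1 calculation, by a two-sample t-test at effect size 0.25, two-sided alpha 0.025 and power 0.80, needs 305.4 evaluable per arm, rounded up to 306. Allowing for 20% dropout, 306 / 0.8 = 382.5, rounded up to 383. So 383 is the number randomized, and its evaluable counterpart is 383 × 0.8 = 306.4. Power for Aim 1 at 306 per arm is 80.1%, as stated.

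**Step 2: Aim 3 power.** With n per arm, np participants in the elevated subgroup and n(1−p) in the other, the variance of the difference between the two subgroup treatment effects is 2/(np) + 2/(n(1−p)). Hence

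SE = √(2 / (n·p·(1−p))), power = Φ(0.5/SE − 1.96).

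| n per arm | p | SE | 0.5/SE − 1.96 | Power, formula | Power, simulation (10,000 runs) | Plan |
|---|---|---|---|---|---|---|
| 306 | 0.35 | 0.1695 | 0.990 | 83.9% | 84.0% | 84% |
| 306 | 0.45 | 0.1625 | 1.117 | 86.8% | 85.9% | 86% |
| 383 | 0.35 | 0.1515 | 1.340 | 91.0% | 90.5% | 84% |
| 383 | 0.45 | 0.1453 | 1.482 | 93.1% | 92.9% | 86% |

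The plan's figures are reproduced at 306 and not at 383. Other readings do worse. With 383 per arm and two-sided alpha 0.025 the results are 85.5% and 88.5%. A one-sided test at 0.05 gives 90% and 92% at 306, and 95% and 96% at 383. Of the combinations tried, only 306 per arm at two-sided 0.05 brings both figures within two points. Solving backwards, 84% implies 307 per arm and 86% implies 299 per arm. For the latter, a margin of one point either way spans 290 to 308.

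**Step 3: the averages.** 0.35 × 0.5 = 0.175 and 0.45 × 0.5 = 0.225; reaching 0.25 would need p = 0.50. However, the formula in Step 2 contains only the difference of 0.5. Adding a constant to both subgroup effects cancels in the interaction contrast. Simulation at 306 per arm confirms this. Effects of 0.075 and 0.575 at 35% prevalence, which do average 0.25, give interaction power 84.0%, against 84.0% for 0 and 0.5. At 45% prevalence, 0.025 and 0.525 give 86.5%, against 85.9%. The differences are within simulation error.

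**Step 4: the subgroup wording.** The same paragraph gives a separate cut-off for each scale (above 11 on the HADS, 9 or more on the COMM), a separate power for each, and applies its conclusion to each of two subgroups. Two separate interaction tests are meant.

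**The case for a change.** The best case for a change is that the Aim 3 paragraph opens with its own sample size and alpha, so a reader is entitled to treat those as the complete inputs, and as written they do not return the stated output. Aim 3 is a formal study aim with a directional hypothesis, and the sponsor undertakes in Section 9.1 to share code and materials so that the work can be replicated. It can also be said that the Aim 1 and Aim 3 assumptions should be labelled as separate scenarios. If the 0 and 0.5 pattern were literally true, Aim 1 power at 306 per arm would be about 47% (overall effect 0.175) or about 70% (0.225).

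The first part stands as an observation: the paragraph does not repeat the dropout allowance. But the allowance is given one paragraph earlier, in the same sentence that introduces 383, and applying it recovers both figures. Sections 5.4.2 and 8.2 also refer to appendices for the sample size calculation and the detailed analysis plan. Those appendices are not in the text reviewed, so it cannot be said that the step is undocumented.

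The second part does not stand. The plan sets a difference that it wishes to be able to detect and uses 0.25 only to explain why 0.5 was chosen. Powering separate aims under separate scenarios is ordinary practice. The 47% and 70% arise only from joining two scenarios that the plan does not join; the 80% for Aim 1 is conditional on 0.25, and on that condition it is correct.

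**Conclusion.** No change follows. The stated 84% and 86% are correct for 383 randomized and about 306 evaluable per arm, assuming a two-sided 0.05 test and unit standard deviation. They are the cautious figures: with no dropout the power would be about 91% and 93%, so the claim of at least 80% holds either way. The averages of 0.175 and 0.225 contradict nothing that the plan asserts and have no bearing on the interaction power. The loose subgroup wording is settled by the rest of its own paragraph. The one thing left out is a repeated mention of dropout, which a statistician checking the figures would supply from the preceding paragraph. Adding it would leave sample size, stated power, conduct, analysis and interpretation as they are.
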